8.1 Steps in Study Visit

Subjects meeting all of the inclusion criteria and none of the exclusion criteria will be asked to provide informed consent. Only after informed consent has been obtained, may the study procedures begin.

8.1.1 Informed Consent Process

Study participation is voluntary. Potential subjects, and/or their legal representatives, are given the most current IRB-approved consent form) to read. They will be provided ample time for review and an opportunity to ask questions about the study. If they agree to participate, they will sign the consent form and be given a copy of the signed document for their records. The original signed copy of the consent form will be retained by the Principal Investigator. Each of these actions/steps will be documented. Only after Informed Consent has been obtained, may the study procedures begin.

8.1.2 New Information About the Study

As this study only requires a one-day visit and there is no follow up, it is unlikely that any new information will influence a subject's decision to participate. However, as ultrasound technology is constantly evolving it may be necessary from time to time to update the consent form so the subject may be informed of any new information. This will be done in conjunction with IRB approval, as appropriate.

8.1.3 Inability to Provide Consent

For this study, eligible subjects must be willing and physically able to undergo all study procedures. If they are unable to provide consent, they may not participate.

8.1.4 Demographics and History

Standard subject demographics (e.g., age, gender, race and ethnicity) and medical history will be collected.

8.1.5 Ultrasound Exams: Remote Viewing and Remote Control

All subjects are indicated for a medically-necessary routine ultrasound exam and will undergo this exam as conducted by a qualified ultrasonographer. Using the Collaboration Live software installed on the ultrasound system, the study investigator will remotely view the exam, including images acquired, in real time. As necessary, the investigator may use the system's capabilities (including text, voice, screen share and webcam video) to provide feedback to the ultrasonographer. The investigator or delegates will also provide assessment regarding use of the Collaboration Live software on a 5-point (Likert) scale, including:

Protocol		Document Title:	Protocol Date:	
Study Number:	10649	Collaboration Live Clinical Study	24Oct2019	Page 9 of 18

- Streaming and image quality
- Ease of use
- Overall experience

The Collaboration Live software's remote control capability will also be used to adjust system settings during the exam. Systems settings may be adjusted by the investigator to assist in the following tasks:

- Image optimization (e.g., image depth, focal depth, gain)
- Pulsed-wave or Color Doppler Imaging
- M-Mode Imaging

To assess the primary endpoint, clinical acceptability, the investigator and qualified ultrasonographer will monitor the system response relative to input changes and record any adverse events occurring during remote control.

8.1.6 Remote Patient Consult

Following the ultrasound exam, the investigator will use the Collaboration Live software's remote control capability to review acquired images with the patient and/or ultrasongrapher. The investigator will also consult the patient using the system's audio and video capabilities.

Study subjects will be asked to complete a Telemedicine Satisfaction Questionnaire to capture feedback regarding information related to use of the Collaboration Live software in remote patient consult. The time spent in the remote consult and the distance (in miles) between the patient and consulting physician will be recorded. Billing data will be evaluated to assess impact of remote consultation on reimbursement.

8.1.7 Additional Measures

Additional information as assessed by the investigator or delegates will be reported throughout the exam, remote control evaluation, or remote consult, including:

- Adverse events, including seriousness and potential relationship to the study device or study procedure
- Technical issues using the Collaboration Live system
- Success rates for key tasks in the collaborative ultrasound exam, including:
 - Establishing remote connection
 - Establishing text chat
 - o Establishing voice call
 - Establishing webcam feed
 - Establishing screen share
 - Establishing remote control

8.1.8 Adverse Events Reporting

The Principal Investigator or delegate must report any Adverse Events (AE) from the time the subject signs the Informed Consent Form until the conclusion of the study-related activities.

8.1.9 Subject Compensation

Subjects will receive compensation for their participation in the study.

8.1.10 Subject Dismissed

After the study scan, remote consultation and patient questionnaire have been completed, subjects are dismissed. No follow up is planned.

Protocol	10649	Document Title:	Protocol Date:	
Study Number:	10649	Collaboration Live Clinical Study	24Oct2019	Page 10 of 18

8.1.11 Study Termination

This study may be suspended or terminated at any time, at the will of the Sponsor.

8.1.12 Sponsor Representatives

None of the study procedures will be completed by Philips representatives. Philips representatives will be available during the study to provide training on the Collaboration Live software and to ensure connectivity.

8.2 Device Accountability

The site will document receipt/return and disposition of investigational products using the product accountability log.

9 Selection and Withdrawal of Subjects

9.1 Selection of Subjects

Subjects will be enrolled based on these inclusion/exclusion criteria. The Principal Investigator is responsible for screening all subjects to determine the eligibility for participation.

Inclusion Criteria:

- 1. Subject is at least 18 years of age
- 2. Subject in indicated for a routine OB/GYN ultrasound examination at the site.
- 3. Subject is willing and capable of providing informed consent and participating in this study.

Exclusion Criteria:

1. A medical condition or co-morbidity that would be unduly affected by study participation, per investigator discretion.

9.2 Vulnerable Populations

The research subjects for this study will include pregnant women. Participation in the study will require informed consent, as described in Section 8.1.1 and the study will be reviewed by an Institutional Review Board (IRB). Ultrasound imaging is based on non-ionizing radiation and is generally considered safe when used appropriately by trained health care providers. The investigational software (Collaboration Live) is intended to facilitate remote viewing or remote control of the EPIQ 5 and EPIQ 7 Ultrasound Systems (software version 5.0.2) which has been FDA cleared.

9.3 **Point of Enrollment**

Potential study subjects meeting all inclusion criteria and none of the exclusion criteria will be asked to provide informed consent. Potential subject whom agree to provide informed consent are considered to be enrolled in the study.

9.4 Withdrawal of Subjects

Study participation is voluntary. The subject may refuse to consent or may withdraw from the study at any time without penalty or loss of benefits to which he/she is otherwise entitled.

The Investigator may discontinue a study subject's participation in this study without his/her consent. If, in the opinion of the investigator, the health or safety of a subject is affected adversely by participation in the study, the subject will be removed.

Protocol		Document Title:	Protocol Date:	
Study Number:	10649	Collaboration Live Clinical Study	24Oct2019	Page 11 of 18

All subjects completing the study will be included in the primary endpoint analysis. No follow-up is required beyond the initial study visit and therefore, no loss to follow-up or withdrawal is anticipated. However, if subject withdrawal were to occur prior to evaluation of clinical acceptability, additional subjects will be enrolled to compensate for the withdrawn subjects.

10 Management of Subjects

The subject's involvement in the study includes the OB/GYN ultrasound exam, remote consultation and patient questionnaire. No study follow-up visits are planned.

There are no restrictions to patient participation regarding concomitant medications or treatments.

11 Assessment of Safety and Performance

The variables necessary for evaluation of the primary endpoint and additional measures are specified in the Table 11 below.

Endpoint or Additional Measure	Required Variables		
Primary Endpoint: Clinically Acceptable Performance of Remote Control Functionality	During remote control, it will be recorded whether the system responds to the remote input as intended and without a delay interfering with the conduct of the exam. Additionally, a clinically acceptable exam would result in no adverse events related to the control feature (see Adverse Events below).		
Adverse Events	Adverse events will be reported on the appropriate case report form. The investigator will assess the seriousness of the event and relationship of event to study device and study procedure.		
Assessment of technical issues	Device deficiencies will be reported on the appropriate case report form.		
Success rates for key tasks in the collaborative exam	Success of the following tasks will be recorded:		
	 Establishing the remote connection Establishing text chat Establishing voice call Establishing webcam feed Establishing screen share Establishing remote control 		
Travel reduction attributable to use of Collaboration Live	Distance between the scanning facility and the investigator's location will be recorded (in miles).		
Ease of use	5-point (Likert) scale data will be reported by the investigator.		
User feedback regarding streaming, image quality and overall experience	5-point (Likert) scale data will be reported by the investigator.		

Table 11: Data Required for Assessment of Endpoints and Additional Measures

Protocol		Document Title:	Protocol Date:	
Study Number:	10649	Collaboration Live Clinical Study	24Oct2019	Page 12 of 18

Endpoint or Additional Measure	Required Variables
Patient feedback regarding remote consultation	Telemedicine Satisfaction Questionnaire ¹ (to be completed by subject following remote consultation).
Impact of remote consultation on reimbursement	Submitted charges and reimbursement rates for remote patient consultation will be reported and compared to standard rates for in-person consultation.

¹ Yip MP, AM Chang, J Chan and AE Mackenzie. Development of the Telemedicine Satisfaction Questionnaire to evaluate patient satisfaction with telemedicince: a preliminary study. Journal of Telemedicine and Telecare 2003; 9: 46-50.

12 Sites

This is a single site study being conducted at Perinatal Associates of New Mexico. The site includes multiple facilities under the direction of the Principal Investigator.

13 Risk and Benefit Analysis

The investigational systems have passed quality assurance testing according to international regulatory guidelines; therefore, the risk of using the device is no greater than the standard risk of using any commercially available ultrasound imaging equipment.

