7.1 Endpoints and Additional Measures

The primary endpoint is the percentage of patient exams for which the remote control functionality performs in a clinically acceptable manner, where clinically acceptable is defined as:

- The system responds to the remote input as intended and without a delay interfering with the conduct of the exam. Additionally, a clinically acceptable exam would also result in no adverse events related to the control feature.

Protocol		Document Title:	Protocol Date:	
Study Number:	10649	Collaboration Live Clinical Study	24Oct2019	Page 8 of 18

Additional measures will be evaluated including:

- Adverse events, including investigator assessment of seriousness and relationship to the study device or study procedure
- Assessment of technical issues
- Success rates for key tasks in the collaborative exam
- Travel reduction attributable to use of Collaboration Live
- Ease of use
- User feedback regarding streaming, image quality and overall experience
- Patient feedback regarding remote consultation
- Impact of remote consultation on reimbursement

8 Study Design

This is a prospective, single-arm, clinical study and will enroll 30 subjects undergoing a routine OB/GYN ultrasound examination. No additional interventions or follow-ups to the subject will be conducted as part of the study.

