13.2 Risks Associated with Study Participation

The study involves use of an investigational software solution that allows users to communicate (by text, voice, screen share, webcam video and remote takeover) from an ultrasound system or workstation to a remote destination. The potential risks associated with use of Collaboration Live include interruption of the procedure due to poor connectivity or network performance and exposure of patient data by a remote user.

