15.2 Expedited Reporting

All SAEs must be reported to Philips within 24 hours of the Investigator becoming aware of the event.

Additionally, any medical device deficiencies that might have led to a SAE if:

- suitable action had not been taken;
- intervention had not been made; or
- circumstances had been less fortunate

must also be reported to Philips within 24 hours of the Investigator becoming aware of the event.

Furthermore, any new findings or updates in relation to previously reported SAE or device deficiencies which may have potentially led to SAE must be reported to Philips within 24 hours of the Investigator becoming aware of the new findings or updates.

16 Statistical Methods

Continuous variables will be summarized using the number of non-missing observations, mean, standard deviation (SD), median, minimum, and maximum; categorical variables will be summarized using the frequency count and the percentage of subjects in each category. No formal statistical hypothesis test is planned and the primary endpoint will be presented as descriptive statistics only.

Protocol		Document Title:	Protocol Date:	
Study Number:	10649	Collaboration Live Clinical Study	24Oct2019	Page 14 of 18

The Primary Endpoint is clinically acceptable performance of remote control functionality. A total of 30 subjects undergoing routine OB/GYN exams will be enrolled in the study. Clinical acceptability of the Collaboration Live software will be evaluated for each subject during remote control of the ultrasound system.

A way to describe the statistical properties of the study design is in terms of 95% confidence interval of the true rate of clinical acceptability based on the observed data. Table 16 provides the two-sided 95% confidence interval (CI) for the true rate of clinical acceptability among 30 enrolled subjects using Clopper-Pearson Exact method. If clinical acceptability is observed in all 30 patients, then the 95% exact two-sided lower confidence bound for the rate of such response in this population would be > 80% (with lower bound of 95% CI = 88.4%). Alternatively, it means if the observed acceptability rate is 100%, then the range of 88.4% - 100% will contain the true acceptability rate, with 95% probability.

Table 16: Ninety-five Percent Confidence Intervals for True Rate of clinical accepatability by Observed Acceptability Rate

N	Observed Acceptability Rate	95% CI for True Acceptability Rate
	30/30 (100%)	(88.4%, 100%)
	29/30 (96.7%)	(82.8%, 99.9%)

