	28/30 (93.3%)	(77.9%, 99.2%)
30	27/30 (90.0%)	(73.5%, 97.9%)
	26/30 (86.7%)	(69.3%, 96.3%)
	25/30 (83.3%)	(65.2%, 94.3%)
	24/30 (80.0%)	(61.4%, 92.3%)

All subjects completing the study will be included in the primary endpoint analysis. No follow-up is required beyond the initial study visit and therefore, no loss to follow-up or withdrawal is anticipated. However, if subject withdraw were to occur prior to evaluation of clinical acceptability, additional subjects will be enrolled to compensate for the withdrawn subjects. The study will end when 30 subjects have been enrolled and data collection is complete. The anticipated study duration is three months.

17 Labeling

The investigational device(s), the instructions for use, or the packaging shall indicate that the investigational device(s) is exclusively for use in a clinical investigation, as required by national regulations.

18 Direct Access to Source Data/Documents

A unique source record will be available for each study participant including documentation of the informed consent form review process, HIPAA completion to ensure patient privacy (United States), and medical history. In some cases (e.g., user feedback data may be entered directly into the CRFs, as appropriate. The sponsor will be allowed access to source data to ensure compliance to the protocol.

The investigator(s)/institution(s) will permit study-related monitoring, audits, IRB review, and regulatory inspection(s) by providing direct access to source data/documents.

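### The completer-and-replacement rule ignores cause, so an exam lost because remote control failed can drop out of the primary acceptability rate

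*Protocol*

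**What the plan says.** **Analysis set.** Protocol Section 9.4: "All subjects completing the study will be included in the primary endpoint analysis". Section 16 repeats the sentence. Completion is not defined; Section 8.1.10 only says that subjects are dismissed once scan, remote consult and questionnaire are done.

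**Replacement.** Section 9.4: "if subject withdrawal were to occur prior to evaluation of clinical acceptability, additional subjects will be enrolled to compensate for the withdrawn subjects". Section 16 has the same rule: "if subject withdraw were to occur prior to evaluation of clinical acceptability, additional subjects will be enrolled to compensate for the withdrawn subjects". Neither place distinguishes reasons. Section 9.4 also lets the investigator discontinue a subject, and says that no withdrawal is expected because there is no follow-up.

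**Endpoint.** Section 7.1 defines it as "the percentage of patient exams for which the remote control functionality performs in a clinically acceptable manner". In Table 11 (Section 11) the variable reads: "During remote control, it will be recorded whether the system responds to the remote input as intended". Section 16 adds: "Clinical acceptability of the Collaboration Live software will be evaluated for each subject during remote control of the ultrasound system".

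**Foreseen failure.** Section 13.2 lists "interruption of the procedure due to poor connectivity or network performance" as a risk. Whether the connection and remote control were established is recorded as key-task success (Section 8.1.7, Table 11), an additional measure that no section links to the primary score.

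**Count.** Enrolment is at consent (Section 9.3). Section 16 ends the study at 30 enrolled subjects and introduces Table 16 for the same 30.

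**The concern.** Failing to take control at all is a basic way for remote-control software to fail. A rate over patient exams should count it. A replacement rule that is blind to cause allows such an exam to be exchanged for one that worked, and a variable recorded only while control is active has no stated value for an exam in which control never began. Either way the rate would describe only exams that connected, and the error can run in one direction only. Section 6 says that the results may support regulatory submissions, so what the headline percentage covers should be plain.

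**Working it through.** **Following an exam in which remote control cannot be established**

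1. *The subject leaves or is discontinued before evaluation.* Sections 9.4 and 16 call for a replacement. No sentence keeps the failed exam in the rate. This needs two events: the technical failure and the departure.
2. *The visit continues.* The scan is done on site by the ultrasonographer (8.1.5). If only remote control is down, the consult can still be held: "The investigator will also consult the patient using the system's audio and video capabilities" (8.1.6). The questionnaire can follow. Such a subject can reasonably be called a completer and is then included. Section 7.1 points to not acceptable, since the system did not respond to remote input; Table 11 and Section 16 place the assessment within remote control, and the score is not stated.
3. *A control-related adverse event occurs.* This already fails 7.1 and is recorded for the endpoint under 8.1.5, so it does not trigger replacement.

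**Size**

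Inputs from Section 16: n = 30, two-sided 95% Clopper-Pearson interval. The number of lost exams, k, is an assumption (1 or 2), because the protocol gives none. All other exams are taken as acceptable.

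Formula for x successes in n: lower limit = 2.5% quantile of Beta(x, n − x + 1); upper limit = 97.5% quantile of Beta(x + 1, n − x). When x = n, the lower limit is 0.025^(1/n) and the upper limit is 100%.

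The protocol's own figure: 0.025^(1/30) = 0.8843, that is 88.4%, as stated in Section 16. For 29/30 the lower limit p solves 30·p^29·(1 − p) + p^30 = 0.025; at p = 0.8278 this is 0.02153 + 0.00345 = 0.02498. The upper limit is 0.975^(1/30) = 0.9992. The 29/30 and 28/30 rows of Table 16 are likewise reproduced.

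| k (assumed) | Reported if lost and replaced | Reported if left unscored, not replaced | Counted as failure, 30 analysed |
|---|---|---|---|
| 0 | 30/30: 100% (88.4–100) | 30/30: 100% (88.4–100) | 30/30: 100% (88.4–100) |
| 1 | 30/30: 100% (88.4–100) | 29/29: 100% (88.1–100) | 29/30: 96.7% (82.8–99.9) |
| 2 | 30/30: 100% (88.4–100) | 28/28: 100% (87.7–100) | 28/30: 93.3% (77.9–99.2) |

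Against the replaced case, one exam costs 100 − 96.7 = 3.3 points on the rate and 88.4 − 82.8 = 5.6 on the lower limit. Two cost 6.7 and 88.4 − 77.9 = 10.5.

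**The count of 30**

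With one replacement, 31 subjects have consented and are therefore enrolled under 9.3, while 30 are evaluated. The Section 16 stopping sentence and the Table 16 description then no longer refer to the same 30.

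**The case against.** The case for leaving the text alone has real force.

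- *Completers are included, but the text does not say only completers.* Correct. No sentence removes an evaluated subject who leaves later. Still, no other rule admits non-completers, and replacement presumes that those who leave before evaluation are out.
- *A technical failure is not a withdrawal.* Correct. The exam is medically indicated and performed on site, so a lost connection gives little reason to abandon it. The first route is possible, not expected. However, the reason given for expecting no withdrawal is the lack of follow-up, which does not address a connection failure within the visit.
- *The score is already implied.* Largely so. Section 7.1 speaks of exams, Section 16 of evaluation for each subject, Table 11 lists the item as required, and the edit checks in 19.2 could query a blank. But a query needs an answer, and the protocol does not give one.
- *Scoring conventions belong in the SAP.* This is fair for the score alone. It does not reach the analysis set and the replacement rule, which the protocol itself fixes, twice.
- *Nothing is hidden.* Correct. Failures to connect remain visible as key-task rates and device deficiencies. This limits the harm but does not correct the primary rate.

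**Conclusion.** The point holds as a minor one. The protocol fixes a replacement rule that takes no account of cause, and this can remove a device failure from the primary rate, always in the device's favour. For a visit that continues without remote control, the likely score is clear but unstated.

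The size rests on an assumed count of one or two exams; with none lost, nothing changes. There is no hypothesis test, so neither type I error nor power is affected.

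A reader might infer more than the text supports. The protocol does not direct that device failures be excluded or replaced, and it does not restrict the analysis to completers in so many words. Nor does it take a subject with a control-related adverse event out of the rate. Two such exams would put the lower limit below the 80% mentioned in Section 16, but that figure illustrates the 30/30 case and is not a success criterion.

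**What to change.** These changes concern scoring and counting only, not who is removed from the study.

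- **Sections 9.4 and 16, analysis set:** every enrolled subject in whom a Collaboration Live session for the exam was started or attempted, whether or not the consult or questionnaire was completed, except those replaced under the rule below. A session that could not be started counts as attempted. An evaluated subject stays in, even if he or she leaves later.
- **Section 7.1 and Table 11, score:** not acceptable if remote control could not be established, was abandoned, or was never tried for a technical reason, or if the subject left for a reason related to the device or connection before acceptability could be judged. Interruptions that are restored are judged by the existing 7.1 criteria. List the cause (software or site network) beside the rate.
- **Sections 9.4 and 16, replacement:** only subjects who leave, or in whom remote control is not attempted, for reasons unrelated to the device or connection, before acceptability is evaluated. Report each replacement with its reason.
- **Section 16, count:** refer to 30 subjects in the primary analysis set, both where the study end is defined and where Table 16 is introduced.

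The cost is wording in four places and one added item, the reason for each replacement; the other data are already collected. The rate may be slightly less favourable, site-network failures will count against it, and a few more than 30 subjects may need to consent.
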